6.6 Locations/Facilities

This is a single-site trial that will take place at Yale University (New Haven, CT). Treatments will take place at Yale Psychiatric Hospital (YPH, part of Yale New Haven Hospital; YNHH), Interventional psychiatry services (IPS). Clinical assessments will take place at YPH or virtually via HIPAA compliant technology (e.g. Yale Zoom), as applicable.

7 Statistical Design

7.1 Sample Size Considerations

While to our knowledge there are no analogous studies in the literature to use as a basis for sample size calculation, we used the data from the two active groups of a relatively similar study of open-label vs placebo-controlled citalopram⁷ to calculate sample size for the current study. Based on this data, sample size per arm was calculated as follows¹³:

$$N = 2 \times \left(\frac{z_{1-\alpha} + z_{1-\beta}}{\delta - \delta_0} \right)^2 \times s^2$$

To account for dropouts, we have chosen a sample size of 34 participants (17 per arm) during the two years of the study.

7.2 Planned Analyses

Data will be examined prior to analysis using descriptive statistics, presented as means \pm SD or median (interquartile range) for continuous characteristics, and as frequencies (%) for categorical characteristics.

Where appropriate, randomized groups will be compared on baseline continuous characteristics (e.g. age) using two-sample Welch's t-test or Wilcoxon rank sum test, and on categorical characteristics using the chi-square test or Fisher's exact test as appropriate. Continuous outcome measures will be assessed for normality using histograms and Q-Q plots, and transformations will be applied as necessary. Between groups primary and secondary outcomes (CEQ-6, MADRS and QIDS) will be considered significant using a two-tailed alpha threshold of 0.05.

The primary and secondary outcomes (CEQ-6, MADRS, QIDS) will be compared between groups using a linear mixed model with group (intervention, TAU) included as a between-subjects factor and time (see study timepoints) included as a within-subjects factor. The group by time interaction will be modeled. The correlation between multiple measurements in different timepoints within each subject will be modeled with random effects with the best-fitting model determined using information criteria.

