3.3 Objectives

Primary Objective:

To determine whether a positive presentation before first treatment improves expectation of improvement from treatment in patients receiving esketamine for a depressive episode within 24 hours after the first treatment.

Secondary Objective:

To determine whether a post-treatment debriefing session to provide encouragement and reassurance improves expectation of improvement from treatment in patients receiving esketamine for a depressive episode within 24 hours after the first treatment.

To determine whether a positive presentation result in an improved response from treatment in patients receiving esketamine for a depressive episode as measured by MADRS score within 24 hours after the first treatment.

To determine whether a positive presentation before first treatment, combined with a post-treatment debriefing session after first treatment, result in an improved response from treatment in patients receiving esketamine for a depressive episode as measured by MADRS score by the end of the acute course of esketamine treatment.

4 Study Design

Approach and consent:

Patients who are deemed clinically appropriate for esketamine will be approached for participation in the study. They will be provided with information regarding the study, including that they will be randomized into two groups with the “intervention” group receiving an informative presentation prior to the first treatment. They will be informed that the goal is to assess the effect of this presentation with regard to its ability to provide sufficient and appropriate information surrounding the treatment. Participants will not be informed at the time of recruitment that we hypothesize the content to potentially affect the tolerability and effectiveness of the treatment course. They will be informed about the full nature of the study

at a end of treatment debriefing session at the end of their participation (further details below).

Randomization

Participants will be randomized at a 1:1 ratio into “intervention” and TAU groups, with the intervention group being presented with the presentation prior to the first treatment, and to receive a “debriefing” session within 24 hours after the first treatment. Both groups will otherwise receive treatment as usual during the course.

Intervention

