4.2 Outcome Variables/Endpoints

4.2.1 Primary Outcome Variables/Endpoints

Primary outcome: Group difference in change in question 6 of the CEQ-6 from baseline to after the presentation

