4.2.2 Secondary and Exploratory Outcome Variables/Endpoints

Secondary Outcome: Group difference in change in MADRS score from baseline to 24 hours after first treatment

Exploratory outcomes:

Group difference in change in CEQ-6 from baseline to 24 hours after first treatment and after follow-up session

Group difference in change in MADRS score by the end of the acute series of treatments

Group difference in the side effect profile

5 Study Participants

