6.1 Study Procedures

Potential subjects will be referred to the study team by the interventional psychiatry physician who has seen the patient in clinical evaluation for esketamine, after ascertaining their agreement to be approached for the study. At this time, the patient will be reached out by a study team member and informed about the study.

Screening / Intake Visit

It is estimated the screening intake will take approximately 2 hours. It will consist of the following procedures and assessments and can be completed in up to 5 days:

- a. Informed Consent: A delegated study team member will discuss risks and benefits of participation and review the study overview with the patient as explained above. The patient will sign the informed consent form prior to any study procedures being performed.
- b. Clinical and Demographic Intake (including medical and psychiatric history, medication history, and current medications)
- c. Montgomery-Asberg Depression Rating Scale (MADRS) and Quick Inventory of Depressive Symptomatology (QIDS-SR16)
- d. CEQ-6 questionnaire regarding upcoming treatment course with esketamine
- e. Review of Inclusion/Exclusion Criteria by investigator

Presentation Visit (Intervention group only)

The intervention consists of a short virtual (via Zoom or similar technology) presentation provided to the participants, within 72 hours before the first treatment with esketamine. The presentation includes predetermined slides and content (the presenter will cover the same

slides and topics but will avoid a strict script to retain the personalized feeling of the presentation, an aspect believed to be crucial to the non-specific effects. Further, patients are allowed to engage, ask questions etc.) The presentation will remain factual and provide information from peer-reviewed literature. However, it is designed to convey a strong positive message, highlighting the effectiveness of the treatment. Additionally, a mild and temporary known side effect of the treatment (dysgeusia) will be intentionally highlighted to assess the 4th hypothesis.

Treatment visits:

Both groups will receive the usual treatment and care. Immediately before first and second treatments both groups will complete the CEQ-6 questionnaire. Additionally, the intervention group will complete the presentation feedback form prior to the first treatment. The rest of the treatments (i.e. treatments 3 to 8) will be done without any assessments.

Follow-up visit:

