6.2 Method of Assignment/Randomization

The randomization process in the study will occur after the screening visit and once the eligibility criteria have been checked and it has been determined by the PI that the subject qualifies. The eligible patients will be randomly assigned to either the intervention group or the TAU group with a 1:1 ratio. Randomization will be conducted using the sequentially numbered, opaque sealed envelopes (SNOSE)¹².

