7.2.2 Analysis of Subject Characteristics

Baseline characteristics will be examined using descriptive statistics, presented as means \pm SD or median (interquartile range) for continuous characteristics, and as frequencies (%) for categorical characteristics. Baseline characteristics include age, sex, ethnicity, socioeconomic status, treatment expectation (CEQ-6) and psychiatric symptoms (MADRS, QIDS).

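### Section 7.2 tests the primary CEQ question 6 endpoint as a change score; prespecified adjustment for the screening score would usually sharpen it at almost no cost

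*Combined protocol and SAP*

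**What the plan says.** The primary endpoint in section 4.2.1, repeated in the Synopsis, is "Group difference in change in question 6 of the CEQ-6 from baseline to after the presentation". On the analysis, section 7.2 says "The primary and secondary outcomes (CEQ-6, MADRS, QIDS) will be compared between groups using a linear mixed model", with group as the between-subjects factor and "time (see study timepoints) included as a within-subjects factor. The group by time interaction will be modeled". Within-subject correlation is handled by random effects chosen by information criteria. Section 7 names no covariate. Baseline CEQ-6 and MADRS appear in 7.2.2 only as characteristics to be described.

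Both question 6 values exist in both arms. The CEQ-6 is part of the screening visit, and section 6.1 adds that "Immediately before first and second treatments both groups will complete the CEQ-6 questionnaire". The screening score precedes allocation: "The randomization process in the study will occur after the screening visit and once the eligibility criteria have been checked" (section 6.2). Table 1 shows four CEQ-6 visits: screening, before Treatment 1, 24 hours after dose 1, and before Treatment 2.

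The primary objective in section 3.3 is to find out if the "presentation before first treatment improves expectation of improvement from treatment in patients receiving esketamine for a depressive episode within 24 hours after the first treatment". Section 4.2.2 lists as exploratory "Group difference in change in CEQ-6 from baseline to 24 hours after first treatment and after follow-up session".

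**The concern.** In the planned model, baseline is one level of time and has its own free group difference. The group-by-time contrast for the visit before Treatment 1 then subtracts each arm's baseline mean in full, which fixes the slope on baseline at 1. ANCOVA estimates that slope instead. Unless the correlation and the SD ratio happen to make the true slope close to 1, the fixed slope costs precision.

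With 34 participants, and dropouts already counted in that number (section 7.1), precision on the primary comparison is scarce. The covariate costs nothing to collect.

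A smaller wording matter sits beside this. The objective's time window does not match the endpoint's, and section 7.2 says only CEQ-6, without naming question 6 or the visit that carries the primary test.

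**Working it through.** **Plan's own figure.** Section 7.1 gives a formula and N = 34 but no effect, SD, power or dropout rate, so N cannot be reproduced. The check uses only n = 17 per arm and the two-sided 0.05 of section 7.2.

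**Assumed inputs.** ρ is the correlation between screening and before-Treatment-1 question 6, taken as 0.3, 0.5 and 0.7. k is the before-Treatment-1 SD divided by the screening SD, taken as 0.8 to 1.5. The documents give neither. Table 1 puts screening at day -16±14, so 2 to 30 days before Treatment 1. Data are taken as complete and normal.

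**Step 1: what the planned contrast is.** A random-intercept model with group, time and group-by-time was fitted to a simulated complete data set (17 per arm, four visits). The contrast was 0.7355, and the plain difference in mean change was also 0.7355.

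**Step 2: variances.** With s0 the screening SD and s1 = k·s0:

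- change score: (2/n)(s0² + s1² − 2ρ·s0·s1)
- ANCOVA: (2/n)·s1²(1 − ρ²)·(1 + 1/(2n − 4)), where the last factor is 31/30 at n = 17
- ratio (ANCOVA / change): k²(1 − ρ²)/(1 + k² − 2ρk) × 31/30

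Example, k = 1 and ρ = 0.5: 0.75/1.00 × 31/30 = 0.775.

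| k | ρ = 0.3 | ρ = 0.5 | ρ = 0.7 |
|---|---|---|---|
| 0.8 | 0.519 | 0.590 | 0.649 |
| 1.0 | 0.672 | 0.775 | 0.878 |
| 1.2 | 0.787 | 0.900 | 0.999 |
| 1.5 | 0.900 | 0.996 | 1.031 |

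At equal SDs the reductions are 32.8, 22.5 and 12.2%. Simulation (40,000 trials per cell) gave ratios of 0.671, 0.775 and 0.878. Simulated type I error was 0.049–0.051 for the change score and 0.048–0.052 for ANCOVA.

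**Step 3: worst case against the change score.** The denominator minus the numerator of the first factor is 1 − 2ρk + ρ²k² = (1 − ρk)², which is never negative. The first factor therefore never exceeds 1, and the ratio never exceeds 31/30 = 1.033. With 15 completers per arm the bound is 27/26 = 1.038, and the equal-SD gains are 32.5, 22.1 and 11.7%.

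**Step 4: power for an illustrative difference of 0.8 before-Treatment-1 SD** (no source in the documents; noncentral t). At k = 1, for ρ = 0.3, 0.5 and 0.7, the change score on 32 df has 48, 62 and 83%, and ANCOVA on 31 df has 64, 73 and 88%. At k = 1.5 the two are 60, 73 and 89% against 64, 73 and 88%.

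**Step 5: a comparator with pooled residual variance.** A random-intercept model over four visits has (34 − 2) × 3 = 96 residual df. At k = 1 its power is 50, 64 and 85%. The ANCOVA interval is √ratio × 2.040/1.985 as wide, that is 0.842, 0.905 and 0.963, or 15.8, 9.5 and 3.7% narrower. If the planned contrast keeps the change-score variance with 96 df, then at k = 1.5 and ρ = 0.7 the factor is √1.031 × 2.040/1.985 = 1.043, so the adjusted interval is about 4% wider.

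**Step 6: the mixed-model alternative.** A common-baseline model with a random intercept only was simulated (8,000 trials per cell, all post-screening SDs equal to k times the screening SD). At k = 1 it performs like ANCOVA. At k = 1.5 and ρ = 0.7 its variance is about 1.12 times the change score's with four visits and about 1.15 times with two.

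**The case against.** The planned analysis is valid. The endpoint is defined as a change, and the group-by-time contrast estimates exactly that. This stands: a reader might infer that section 7.2 ignores baseline or is biased, and the documents do not support that. Baseline is subtracted, and both analyses hold their type I error.

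The size of the benefit rests on two quantities the documents do not give. This also stands. At k = 1.2 with ρ = 0.7, or k = 1.5 with ρ = 0.5, the gain is essentially nil. But the loss against the change score is capped at 3.3% with complete data, so the balance favours adjustment.

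A single-visit ANCOVA sits less easily with section 7.7, which relies on all available data and a mixed model under MAR. Anyone without a before-Treatment-1 score would drop out of the test unless imputed. This stands and is met in the fix.

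A reader might infer that any mixed model with a common baseline mean does the same job. It does not: section 7.2 allows a random-intercept structure, and step 6 shows that this can lose about 12 to 15% when the later SD is larger.

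Finally, a reader might infer two rival primary endpoints from the objective's wording. Sections 4.2.1 and the Synopsis state one endpoint in the same words, 4.2.2 labels the 24-hour CEQ-6 exploratory, and 7.3 restates the primary question without a 24-hour window. The mismatch is one of wording.

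**Conclusion.** This is an efficiency improvement and not an error. With complete data, section 7.2 yields a change-score comparison although a pre-randomization covariate is available in both arms. ANCOVA on screening question 6 cuts the variance by about 33, 22 or 12% at correlation 0.3, 0.5 or 0.7 with equal SDs. Across correlation 0.3 to 0.7 and SD ratio 0.8 to 1.5, it runs from a 48% gain to a 3% loss.

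The 3% bound belongs to ANCOVA against the change score, at 17 per arm with complete data. It does not carry over to other adjusted models or to a comparator that pools residual variance over four visits. Against that comparator the gain is smaller, and the interval can be slightly wider at high SD ratios. The arithmetic is firm, while the realised gain depends on the unknown correlation and SD ratio. No figure is claimed for MADRS.

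**What to change.** In 7.2, state that the primary test (two-sided 0.05) is the group effect on CEQ question 6 immediately before Treatment 1, adjusted for screening question 6 by ANCOVA. In 7.7, state that a missing before-Treatment-1 score is handled by multiple imputation, a method that section already names among its sensitivity analyses, so that all randomized participants are kept.

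An acceptable alternative is a mixed model with a common baseline mean and an unstructured covariance, with variances free by visit. A random intercept alone is not enough.

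Treat MADRS at 24 hours in the same way, with baseline MADRS as the covariate.

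Separately, align the time window of the primary objective (Synopsis and 3.3) with the endpoint in 4.2.1.

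The cost is a few sentences in 7.2 and 7.7, one residual degree of freedom (31 instead of 32), and one line in the objectives. No new data or visits are needed. The change should be made before outcomes are examined by group.

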7.2.1 Secondary Objective Analyses

Please see above for the analysis of secondary efficacy outcomes (MADRS and QIDS). To examine the safety and tolerability of the intervention for the duration of the study, we will use descriptive statistics to characterize the rates of these events in the intervention group.

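### The objectives, endpoint list and analysis section name different secondary outcomes, and the unadjusted 0.05 rule in 7.2 makes that label decide which results may be called significant

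*Combined protocol and SAP*

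**What the plan says.** **Primary.** Section 4.2.1 names one outcome: "Group difference in change in question 6 of the CEQ-6 from baseline to after the presentation".

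**Endpoint list.** Section 4.2.2, like the synopsis under Outcome Variables, has one entry above the exploratory items: "Secondary Outcome: Group difference in change in MADRS score from baseline to 24 hours after first treatment". The exploratory items include the later CEQ-6 change and "Group difference in change in MADRS score by the end of the acute series of treatments". Section 7.3 also states a single secondary question, MADRS at 24 hours.

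**Objectives.** Section 3.3, like the synopsis under Objectives, has three secondary objectives: expectation after the post-treatment session, MADRS within 24 hours of treatment 1, and response "as measured by MADRS score by the end of the acute course of esketamine treatment".

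**Analysis.** Section 7.2 says: "Between groups primary and secondary outcomes (CEQ-6, MADRS and QIDS) will be considered significant using a two-tailed alpha threshold of 0.05". Section 7.2.1 points back to that text for the "secondary efficacy outcomes (MADRS and QIDS"). Neither section ties MADRS or QIDS to a visit, and neither gives a testing order or an adjustment. QIDS appears elsewhere as an assessment, but in no objective and no endpoint list.

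**The concern.** Disagreement over labels would be minor if the label had no consequence. Here it has one, because 7.2 attaches the significance threshold to primary and secondary status. Take an end-of-course MADRS comparison with p = 0.03. Under 3.3 it is a significant secondary result; under 4.2.2 it is exploratory. A QIDS result with the same p-value is a significant secondary outcome under 7.2.1 and unlisted under 4.2.2. Nothing says which section governs, so the choice could be made after the results are known.

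Hypothesis 3 is the most exposed. It concerns the presentation combined with the post-treatment session. Section 4 (Study course) places that session after the 24-hour assessments are completed, so 24-hour MADRS cannot reflect it. End-of-course MADRS can, and its status is one of those in dispute.

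**Working it through.** The plan has no multiplicity figure to reproduce. Its only computed number, 34 participants, plays no part in this point. The inputs are the 0.05 two-tailed threshold (7.2), the outcome lists quoted above, and the visits. Table 1 has MADRS and QIDS after baseline at two times: 24 hours after dose 1, and within 72 hours after the 8th treatment.

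**Step 1: count the secondary results by source.**

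| Source | Secondary results | Number | With the primary |
|---|---|---|---|
| 4.2.2, 7.3, synopsis outcomes | MADRS 24 h | 1 | 2 |
| 3.3, synopsis objectives | CEQ-6 after session, MADRS 24 h, MADRS end | 3 | 4 |
| 7.2 and 7.2.1, one test per scale | MADRS, QIDS | 2 | 3 |
| 7.2 and 7.2.1, scale by visit | MADRS and QIDS, each at 24 h and end | 4 | 5 |
| Union of all sections | the four above plus CEQ-6 after session | 5 | 6 |

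At the level of scale and visit, only MADRS at 24 hours is in all three lists. The primary belongs in the last column because 7.2 applies the same threshold to it.

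**Step 2: familywise error if the k tests were independent.** The formula is 1 − 0.95^k, and the upper bound under any dependence is k × 0.05.

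- k = 2: 1 − 0.95² = 0.0975 (bound 0.10)
- k = 3: 0.143 (bound 0.15)
- k = 4: 0.185 (bound 0.20)
- k = 5: 0.226 (bound 0.25)
- k = 6: 1 − 0.95⁶ = 0.265 (bound 0.30)

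**Step 3: sensitivity to correlation.** MADRS and QIDS rate the same condition in the same patients, so independence is not realistic. No document gives a correlation. If a common correlation of 0.5 is assumed purely for illustration, two tests give about 9% and six give about 21%.

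**Step 4: sensitivity to the counting rule.** Section 7.2 does not limit CEQ-6 to question 6 or to one visit. Table 1 has three post-baseline CEQ-6 times, so counting every scale-by-visit contrast gives 3 + 2 + 2 = 7 and 1 − 0.95⁷ = 0.302. In the other direction, one group-by-time test per scale gives three tests in total (0.143).

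**Step 5: after the fix.** With question 6 and then 24-hour MADRS tested in fixed order, MADRS can be claimed only if question 6 is significant, and familywise error stays at 0.05. Without an order, the same two tests carry 0.0975 if independent and at most 0.10.

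**The case against.** The best defence is that the core of the hierarchy is stable. The synopsis outcomes, 4.2.1, 4.2.2 and 7.3 agree on expectation as primary and 24-hour MADRS as secondary. Section 2.1 calls this an initial study to support later proposals, and 9.8 describes a pilot award. How strictly to control error over secondary outcomes in such a study is partly a matter of judgement. This stands as a reason not to rate the point higher. It does not remove the contradiction, because the plan itself chose to attach a significance rule to secondary status.

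A second objection concerns the count, and it also stands. A reader might infer that the plan allows anywhere from one to five results to be claimed at 0.05, with false-positive risk rising from 5% to 22.6%. The documents do not support that. One and five are counts of secondary results only, whereas 7.2 tests the primary at 0.05 as well. Five is a union that no single section yields; the most from one section is four. Even four assumes a separate test at each visit, while 7.2 describes a mixed model with a group-by-time interaction that could be read as one test per scale.

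Third, making the endpoint list govern leaves Hypotheses 2 and 3 with exploratory endpoints. That is a real cost, and an amendment should state it openly.

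**Conclusion.** The point holds as an inconsistency in the current text with a consequence for inference. The sections disagree on the status of end-of-course MADRS, post-session CEQ-6 and QIDS, and 7.2 makes that status decisive. Counting the primary, the plan supports between two tests at 0.05 (endpoint list) and six (union of sections). The corresponding familywise error is 9.75% to 26.5% if the tests were independent, and lower if they are positively correlated. These figures illustrate the spread and are not estimates of the trial's actual error rate. They rest on the counting rule in the table and on independence, and any correlation value would be an assumption. The standing of the primary outcome is not in question. The change should be made, but it does not threaten the trial's main comparison.

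**What to change.** Before outcomes are examined by group, put one hierarchy, with scale and timepoint for each entry, in the synopsis (both lists), 3.3, 4.2.2, 7.2 and 7.2.1.

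The smallest change is the hierarchy already in 4.2.2 and 7.3:

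- Primary: CEQ-6 question 6, baseline to after the presentation.
- Only secondary: MADRS, baseline to 24 hours after treatment 1. Test it after the primary in fixed order at two-tailed 0.05 if familywise error is to stay at 5%.
- Exploratory: QIDS at both visits, later CEQ-6, and end-of-course MADRS, reported as estimates with 95% confidence intervals and no significance claim.
- Limit the 0.05 sentence in 7.2 to the primary and the one secondary. Relabel the two other secondary objectives in 3.3 and the synopsis, and drop QIDS as a secondary efficacy outcome in 7.2.1.

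This needs a protocol amendment, but no new data, visits or participants. The cost is that fewer outcomes can be called significant, and that Hypotheses 2 and 3 are then tested only in an exploratory way. If the sponsor prefers to keep end-of-course MADRS as secondary for Hypothesis 3, list it as such in 4.2.2 and add it to the testing order. The requirement is that every section gives the same list.
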